3. What are the effects of Sum Sanos on fruit and vegetable intake, physical activity levels, blood pressure, waist circumference, health-related quality of life, habit-strength, and self-regulation of eating behaviour at 3, 6, 12 and 24 months, and how do these compare with the 7SH interventions?
4. Is there a relationship between individual temperament and BMI, weight change, habit-strength, health-related quality of life and self-regulation of eating behaviour?
5. What is the relationship between the number of coach-appointments and weight loss?

Objective: The objective of this trial is to assess the effectiveness of a coach-led (Sum Sanos) compared with two self-directed (7SH booklet and app) habit-based interventions on 12-month weight loss outcomes in adults with overweight or obesity.

Hypothesis: We hypothesise that Sum Sanos will be superior for weight loss outcomes compared with 7SH booklet and 7SH app.

Study arms: Sum Sanos vs Seven Savvy Habits Booklet vs Seven Savvy Habits App

Study design: Open-ended, multi-site, 3-armed randomised controlled trial. This is a superiority trial.

Methods: participants, interventions and outcomes

Study setting: This trial will be conducted in the community on the Gold Coast, Australia. Data collection will take place at a Bond University.

Eligibility Criteria: Eligible participants will be aged between 18 and 65 years, have a BMI ≥ 27.0 kg/m², own a smartphone, able to consent for themselves and able to attend all required appointments during the intervention period. Participants will be recruited regardless of obesity-related comorbidities (e.g., cardiovascular disease and diabetes). Exclusion criteria includes participants who are pregnant, significantly ill, participating in other weight management programs, expecting to have bariatric surgery in the next 24-months, or taking medications affecting appetite, metabolism or weight.

Interventions: There are three intervention groups in this trial.

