	Qualitative interviews						x	

Sample size: We aim to observe a difference between Sum Sanos and 7SH intervention groups at 12-months from baseline. Sample size calculations were based on mean weight loss and standard deviation from previous trials using a similar intervention to 7SH. Our power calculation suggests 35 participants are required in each of the 3 arms to achieve a 90% power and 5% significance criterion to detect a 4kg (SD 5.03) difference between Sum Sanos and 7SH intervention groups at 12 months. To account for 30% attrition, we will recruit 138 participants.

Recruitment: The research investigators will recruit participants through local public relations, including newspaper, television and radio advertisement and through social media. Our study timeline has allowed 3 months to recruit the required sample size. The recruitment progress will be monitored on a weekly basis. If the number of enrolled participants is not reaching key milestones, additional public relation outputs will be instigated.

Methods: assignment of interventions

Allocation: Computer generation randomisation will occur after baseline assessment to allocate participants to either Sum Sanos, 7SH-B or 7SH-A (allocation ratio 1:1:1). After a 1-week run-in period, participants will be informed of their study group allocation via telephone by the primary investigator. We will use minimization stratified on, BMI categories (overweight, obese class I, II, III), age (18-30, 31-43, 44-56, 57-65 years); and gender.

Implementation: Individuals interested in participating in the trial will email through their expression of interest using the contact details specified in the media advertisements. The primary investigator will speak with each individual over the phone to conduct initial screening against the eligibility criteria. If eligible, individuals will meet with the research assistant at the relevant university, to provide written consent and baseline measurements. Ineligible individuals will be recommended to see their local health care provider for weight management support.

One week after recruitment to the trial, the primary investigator will randomise participants into one of the three study arms using the clinical trial management software package, MASCoT (<https://mascot.org.au>). Participants will be informed of their allocation via telephone call from the primary investigator.

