Statistical methods: Analysis of covariance (ANCOVA) will be used for analysis of pre-post continuous measures collected during the study. For the primary outcome of change in weight at 12 months we will use linear regression to compare change in weight from baseline to 12 months with adjustment for baseline weight. We will use a type 3 analysis of effects to test the null hypothesis of no difference between the 3 treatment groups. If there is evidence of a difference ($P < 0.05$), further pairwise comparisons between groups will be undertaken. Similar analyses will be undertaken for other continuous pre-post outcomes. Treatment effects will be reported as mean differences with 95% confidence intervals.

We plan to finalise and publish a detailed statistical analysis plan (SAP) prior to completion of data collection and before any statistical analysis is undertaken.

Additional analyses: In addition to the primary analysis outlined above we will conduct an adjusted analysis of the primary outcome to assess the impact of any potential baseline imbalances between treatment groups that may have occurred by chance. Variables to be included as covariates for this analysis include treatment site (included as indicator variables), gender and age. BMI will not be included as it is highly correlated with baseline weight which is already included in the ANCOVA regression model.

Handling missing data: We will conduct intention-to-treat analysis. To account for missing primary outcome data, we will implement multiple imputation. In an additional analysis of the primary outcome we will use a per-protocol strategy to compare treatment groups after excluding participants who did not follow the study protocol.

Methods: Monitoring

Harms: Although we do not anticipate harms in this trial, participants are provided with the contact details of the primary investigator prior to recruitment and encouraged to make contact if they experience any harms, discomforts or adverse events. Participants may also discuss harms with the research assistant during data collection appointments. They may also speak with the primary investigator (7SH groups) or health coach (Sum Sanos) during the follow-up calls. An open-ended discussion on consequential events will be discussed during the 12-month interviews.

Ethics and dissemination

Research ethics approval: Ethics approval will be sought from the Bond University Human Research Ethics Committee in Australia.

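### The 90% power is for one Sum Sanos vs 7SH comparison, while the hypothesis names two and the analysis makes both conditional on a 3-group test; winning both has about 84% power

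*Protocol*

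**What the plan says.** Four statements in the protocol bear on this point.

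- **Hypothesis:** "We hypothesise that Sum Sanos will be superior for weight loss outcomes compared with 7SH booklet and 7SH app". Two comparators are named.
- **Sample size:** the section asks for 35 per arm, at 90% power and a 5% level. The stated target is "to detect a 4kg (SD 5.03) difference between Sum Sanos and 7SH intervention groups at 12 months". This is one difference, with no mention of two contrasts or of a preceding test. On dropout the section adds: "To account for 30% attrition, we will recruit 138 participants".
- **Statistical methods, test:** the primary analysis is a linear regression of 12-month weight change on group, adjusted for baseline weight, with a type 3 test across the three groups. If that test gives P < 0.05, "further pairwise comparisons between groups will be undertaken".
- **Statistical methods, reporting:** "Treatment effects will be reported as mean differences with 95% confidence intervals". This sentence carries no condition.

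The protocol does not say whether the hypothesis is confirmed by winning both contrasts or only one. It promises a detailed SAP before data collection is complete and before any analysis.

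**The concern.** The hypothesis, the power calculation and the analysis each imply a different test. The hypothesis points to two contrasts, the sample size to one, and the analysis to a 2-degree-of-freedom overall test that also includes booklet versus app, a comparison outside the hypothesis. The stated 90% therefore does not describe the chance of confirming the hypothesis as worded.

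The second issue is estimation. In a three-arm trial the treatment effects that answer the primary question are the pairwise mean differences. If pairwise comparisons are withheld whenever the overall P value is 0.05 or more, a result of P = 0.06 would leave Sum Sanos versus booklet and Sum Sanos versus app unreported. That is when their confidence intervals would be most informative. The reporting sentence points the other way, so the section does not settle what happens.

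**Working it through.** **Inputs (Protocol, Sample size):** difference 4 kg, SD 5.03, 5% significance, 90% power, 35 per arm, 30% attrition, 138 recruited; allocation 1:1:1. Sidedness is not stated.

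**1. Reproduce the 35.** Standardised effect: 4 / 5.03 = 0.795. For a two-sample t-test with 35 per arm, the noncentrality is 0.795 × √(35/2) = 3.33. The exact two-sided 5% power is 90.65%; with 34 per arm it is 89.8%. So 35 is the smallest size that reaches 90%. The alternatives, by the normal approximation (which gives 34 for the plain two-sided test), do not fit: one-sided needs 28, Bonferroni for two contrasts 40, and for three contrasts 43. The stated figure is one unadjusted, ungated, two-sided comparison.

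**2. Completers per arm.** 138 / 3 = 46 per arm, which is 35 × 1.3 = 45.5 rounded up. After 30% attrition, 46 × 0.7 = 32.2, or about 32 per arm. Keeping 35 would need 35 / 0.7 = 50 per arm, or 150 in total. The calculations below are therefore given at 35 and at 32.

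**3. Overall test.** With means 4, 0, 0 the grand mean is 4/3 and the sum of squared deviations is (8/3)² + 2 × (4/3)² = 10.67. The noncentrality is n × 10.67 / 5.03², which is 14.76 at 35 and 13.49 at 32. The noncentral F gives power of 93.4% and 90.9%. The chance of a non-significant overall test at the design effect is thus 6.6% or 9.1%.

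**4. Pairwise contrasts.** Simulation with 400,000 trials per sample size, means 4/0/0, SD 5.03, variance pooled over three arms, two-sided 5% tests:

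| Success rule | 35 per arm | 32 per arm |
|---|---|---|
| One named contrast, no gate | 90.9% | 88.3% |
| One named contrast, through the gate | 88.8% | 85.6% |
| Both contrasts, no gate | 84.6% | 80.7% |
| Both contrasts, through the gate | 84.3% | 80.2% |
| At least one contrast, through the gate | 93.3% | 91.0% |

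**5. Split the loss.** At 35 per arm, requiring both wins takes power from 90.9% to 84.6% (6.3 points). Adding the gate takes it to 84.3% (under 0.5 points). The further fall to 80.2% comes from having 32 rather than 35 completers (about 4 points).

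**6. Sensitivity.** This case is an assumption and is not in the protocol: one 7SH arm lies halfway, so the true differences are 4 and 2 kg. The 4 kg contrast then has 91% power without the gate and 84% with it at 35 per arm (88% and 80% at 32). The gate costs more when the two 7SH arms differ.

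**The case against.** The strongest reply is that the only decision rule written down is the 3-group test, and its power is 93% at 35 per arm and 91% at 32, so the stated 90% is met for the declared primary test. That stands. A reader might infer that the trial's real power is 80-84%, but the protocol fixes no both-must-win rule; the figure holds only if the hypothesis is read that way. For one named contrast through the gate, power is about 89% or 86%.

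A reader might also blame the gate for the loss. Under the protocol's own assumption of a single 4 kg difference, the gate costs under 0.5 points of joint power and about 2 to 3 points on one contrast. The larger cost in the halfway case rests on an assumption that the protocol does not make; it describes the app as presenting the same seven strategies as the booklet. The 80% figure likewise needs the attrition shortfall and does not follow from the hypothesis and gate alone.

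It is also tempting to say that a null overall test leaves the primary question without estimates. The unconditional reporting sentence does not support that as fact; it is one reading of an ambiguous section. Nor is there a type I error point, because with three arms a significant overall test followed by unadjusted pairwise tests controls the family-wise error rate.

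Finally, the success rule could be left to the promised SAP. That is fair for the detail, but the hypothesis, the power statement and the gate are all in the protocol and do not match one another.

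**Conclusion.** The point holds in a conditional form. The 90% belongs to one ungated pairwise t-test. If the hypothesis requires Sum Sanos to beat both 7SH arms, power is about 84% at 35 per arm, almost entirely because two wins are needed, and about 80% at the 32 completers that the recruitment target implies. Separately, Statistical methods conflicts with itself on whether the two contrasts are estimated after a non-significant overall test, an event with 7-9% probability at the design effect and more if the true effect is smaller.

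Assumptions: SD 5.03 is the residual SD of weight change, with no gain from baseline adjustment; the true advantage is 4 kg over each 7SH arm; and multiple imputation recovers no information from dropouts. This should be corrected, but it does not undermine the design.

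**What to change.** In the protocol, or in the SAP before any analysis:

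1. Name Sum Sanos vs 7SH-B and Sum Sanos vs 7SH-A as the primary contrasts.
2. Report both mean differences with 95% confidence intervals whatever the overall test shows. The planned regression already yields them.
3. State whether the hypothesis is confirmed only if both contrasts favour Sum Sanos at 5%. A both-must-win claim needs no further alpha adjustment. If one win is to suffice, keep the overall test as the gate or specify an adjustment.
4. Restate power for the chosen rule. For both contrasts it is about 84% at 35 per arm and about 80% at 32.

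The cost is wording and a less favourable stated power, with no extra participants. Should the sponsor instead want 90% for both contrasts, about 41 evaluable per arm are needed: 41 / 0.7 = 58.6, so 59 per arm and 177 recruited. That is a separate choice and not required by this correction.

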- A. Sum Sanos™ (<https://www.sumsanos.com/>) is a 12-month, one-on-one, Coach-supported program. Participants meet with a Sum Sanos™ Health Coach monthly (either in a public place or the coaches' office), for 1 hour face-to-face or video call and receive a weekly 10-minute follow-up phone call. Each month, the participant will be presented with a new module to discuss with their Coach. Module topics include: goal setting, forming new habits, breaking old habits, mindful eating and setback strategies, to name a few.
- B. Seven Savvy Habits Booklet (7SH-B) is a program which aims to increase habitual performance of 7 proven weight management strategies, such as: reducing non-hungry eating, drinking water before meals and being active for at least 30 minutes a day, to name a few. The habits are presented in the form of a booklet, and a tracking diary is provided for self-monitoring of the habits. Participant are required to try and perform as many of the 7 habits as they can, everyday for 12 months. To support participants on the program and reduce attrition, they will receive follow-up phone calls by a member of the research team (monthly for the first 3 months then once every 3 months till the end of the intervention period).

- C. Seven Savvy Habits App (7SH-A) presents the same 7 proven weight management strategies as the 7SH-B, but the habits are presented via a smartphone application, instead of a booklet. The tracking diary for self-monitoring of the habits is embedded within the app. Participants are required to try and perform as many of the 7 habits as they can, everyday for 12 months. To support participants on the program and reduce attrition, they will receive follow-up phone calls by a member of the research team (monthly for the first 3 months then once every 3 months till the end of the intervention period).

Adherence: Participants in the three intervention groups will be provided with a tracking diary for self-monitoring. Sum Sanos participants will present the diary to their coaches at their monthly meeting. They will also have weekly contact with their coach which shows increased adherence through support and accountability.

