Health-related quality of life: The Short Form-12 (SF-12) is the most commonly used and most valid and reliable health measure for assessing health-related quality of life ⁷. The 12 questions include: 2 questions concerning physical functioning; 2 questions on role limitations because of physical health problems; 1 question on bodily pain; 1 question on general health perceptions; 1 question on vitality (energy/fatigue); 1 question on social functioning; 2 questions on role limitations because of emotional problems; and 2 questions on general mental health (psychological distress and psychological well-being) ⁸.

Fruit and vegetable intake: Following Australian dietary guidelines, fruit and vegetable intakes were measured as a count of serves, from 0 to 3+ for fruit and 0 to 5+ for vegetables ⁹. Participants are simply asked, “How many serves of fruit/vegetables, do you eat on a typical day?” ¹⁰.

Exercise: Following a similar scale to fruit and vegetable intake, physical activity will be recorded as hours of exercise performed per week (1-item); “How many hours of exercise do you do in a typical week?”.

Coach sessions attended: The number of coach sessions attended (Sum Sanos) will be recorded by the health coaches and reported back to the primary investigator at 3, 6, and 12-months.

Habits achieved: The number of habits achieved (7SH-B and 7SH-A) will be recorded by the participant and reported back to the primary investigator at 3, 6, and 12-months)

Post-intervention qualitative interview: Using a maximum variation design, a selected group of participants will be invited to take part in a post-intervention interview. Semi-structured qualitative interviews will be conducted to explore participants’ general experience on the interventions. Interviews will be audio-recorded with participants’ consent, transcribed and thematically analysed. The interviews will be modelled based on a previous study conducted by the primary investigator ¹¹.

Baseline only:

Demographic information: General demographic and medical history will be collected at baseline using the participant registration form (attached).

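### Harms rest on voluntary reports at programme contacts about 9 to 11 times more frequent in Sum Sanos than in each 7SH arm, so any harms reported by arm would be open to ascertainment bias

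*Protocol*

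**What the plan says.** The Harms paragraph under Methods: Monitoring names four routes.

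- **Participant-initiated contact, all arms.** Participants hold the primary investigator's contact details and are "encouraged to make contact if they experience any harms, discomforts or adverse events".
- **Data collection appointments, same schedule in all arms.** Participants may raise harms with the research assistant.
- **Follow-up calls, different by arm.** "They may also speak with the primary investigator (7SH groups) or health coach (Sum Sanos) during the follow-up calls".
- **Interviews.** "An open-ended discussion on consequential events will be discussed during the 12-month interviews".

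The Interventions section sets the contacts. Sum Sanos "is a 12-month, one-on-one, Coach-supported program", with monthly meetings "for 1 hour face-to-face or video call and receive a weekly 10-minute follow-up phone call". Both 7SH arms are called "monthly for the first 3 months then once every 3 months till the end of the intervention period". Under Post-intervention qualitative interview, "a selected group of participants will be invited to take part in a post-intervention interview".

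Table 2 schedules questionnaires for every participant at baseline, 3, 6, 12 and 24 months and has no harms item. Harms are not in the list of outcome measures, and no comparison of harms between arms is stated.

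**The concern.** When harms are volunteered rather than asked about, the number recorded depends on how often a participant has someone to tell, and on who that is. Both differ by arm here. A Sum Sanos participant speaks weekly to a health coach, who is assigned by the programme's parent company (Implementation). A 7SH participant is called six times in the year and, according to the Harms section, speaks to the primary investigator. The protocol answers the declared interest with blinded data collection and blinded analysis (Declarations of interests), but a harm told to a coach on a call lies outside that safeguard.

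If the report of this randomised trial shows harms by arm, the counts would mix true occurrence with opportunity to report. This is a matter of data collection. A statistical analysis plan can choose how to tabulate what was recorded, but it cannot recover answers to a question that was never put to everyone.

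**Working it through.** The protocol states no contact ratio and no harm rate, so there is no stated figure to reproduce. The check is a count of scheduled contacts over the 12-month programme.

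**Inputs (Interventions A, B and C; Outcome measures; Table 2)**
- Sum Sanos: 12 monthly meetings and about 52 weekly calls. The total is 52 + 12 = 64. It is 52 if only calls count, or if a meeting replaces that week's call (40 + 12).
- Each 7SH arm: calls at months 1, 2 and 3, then 6, 9 and 12, giving 3 + 3 = 6. It is 5 if no call is made at month 12.
- Assessment visits common to all arms: 3, 6 and 12 months within the programme year, and 24 months after it.

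**Ratio of contacts, Sum Sanos to one 7SH arm**

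| Count | Sum Sanos | 7SH | Ratio |
|---|---|---|---|
| Calls and meetings | 64 | 6 | 10.7 |
| 48 calls and 12 meetings | 60 | 6 | 10.0 |
| Calls only, or meeting replaces a call | 52 | 6 | 8.7 |
| Upper count plus 3 common visits | 67 | 9 | 7.4 |
| Lower count plus 3 common visits | 55 | 9 | 6.1 |
| Upper count plus 4 common visits | 68 | 10 | 6.8 |
| Lower count plus 4 common visits | 56 | 10 | 5.6 |

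With only 5 calls in 7SH, programme contacts alone give 52/5 = 10.4 to 64/5 = 12.8.

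**By period.** In months 1 to 3, Sum Sanos has 13 calls, or 16 contacts with the 3 meetings, against 3 calls: 13/3 = 4.3 to 16/3 = 5.3. In months 4 to 12 it has 39 calls, or 48 contacts with the 9 meetings, against 3: 39/3 = 13 to 48/3 = 16. The imbalance is largest in the last nine months.

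**What reaches the trial record.** Under Coach sessions attended, coaches report the number of sessions to the primary investigator at 3, 6 and 12 months. No passage says that they also pass on harms. More frequent contact in Sum Sanos therefore need not mean more recorded events.

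**Two passages set side by side.** The Harms section refers to the 12-month interviews without restriction, while the interview section offers them to a selected group. Separately, the Interventions section assigns the 7SH calls to someone in the research team, whereas the Harms section has 7SH participants speaking to the primary investigator.

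**The case against.** The strongest reply is that two of the four routes are equal. Every participant can contact the primary investigator at any time, and the assessment visits follow one schedule. This stands. It lowers the ratio to about 6 to 7, and it means a reader should not conclude that harms by arm cannot be compared at all. It does not remove the problem: reporting at visits is also voluntary, and the protocol does not say that the source of a report is recorded, so visit reports could not reliably be separated later.

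A second reply is that no between-arm harms analysis is stated and that tabulation belongs in the analysis plan. That also stands, so the point is limited to how harms are collected.

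Three stronger readings are tempting and not supported:

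- **A numerical multiple.** Suppose an event is mentioned only if it is present on a contact date. Six dates would then catch about 6 × 14/365 = 23% of 14-day events, while weekly contact would catch nearly all. That supposes no recall and no unprompted report, and the Harms section invites unprompted reports. The longest gap between 7SH contacts is 3 months, so with recall over that period every event is reportable in both arms and the ratio is 1. The same no-recall rule would give a question at 3, 6 and 12 months only 3 × 14/365 = 12%, so it cannot be used to argue for that question.
- **Events in the 7SH arms will be missed.** With no stated duty on coaches to forward harms, Sum Sanos events may be lost as well. The direction is open.
- **The interviews bias the comparison.** A selected group limits completeness in every arm, but nothing shows that selection differs by arm. The Harms section can also be read as meaning simply the interviews defined elsewhere; the wording needs clarifying and is not a proven error.

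**Conclusion.** The concern holds in a limited form. No route puts the same harms question to every participant, programme contacts are about 9 to 11 times more frequent in Sum Sanos (about 6 to 7 times with the common in-year visits), and call reports go to different recipients. Any harms reported by arm would be open to ascertainment bias.

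The contact ratio rests on 52 weekly calls with or without 12 further meetings, and on six 7SH calls. The size of the resulting bias cannot be derived from the protocol. It ranges from none, with full recall or unprompted reporting, to several-fold without either, and its direction is uncertain. The primary weight comparison is not affected. This is a worthwhile, cheap improvement and not a flaw in the main analysis.

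**What to change.** 1. Add one identical, self-completed harms question to the Qualtrics questionnaire that all arms complete at 3, 6, 12 and 24 months, with a recall period covering the time since the last visit. Because it is self-completed, it does not require a conversation that might reveal allocation to the blinded research assistant.
2. State that any between-arm harms summary uses those answers only.
3. Record the source of every other report, and list spontaneous, coach-reported and interview-reported events separately.
4. Keep the report source from the blinded analyst until the primary analysis is done, because a coach-reported event identifies the Sum Sanos arm.
5. State in the Harms section that the 12-month interviews cover only a selected group.
6. Reconcile the Interventions and Harms sections on who makes the 7SH calls.

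The cost is about a minute per visit, a wording change, and some care in handling the source field. One limit remains: recall over 6 months (to the 12-month visit) or 12 months (to the 24-month visit) will be incomplete. The question and its timing would, however, be the same in every arm, which the present routes do not offer.
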